	same dose level for peripheral isolated n. VII (Bell's palsy)^	
Grade 3	Off protocol therapy	
Grade 4	Off protocol therapy	
Patients with any CNS events including aseptic meningitis, encephalitis, symptomatic		
hypophysitis, or myopathy, peripheral demyelinating neuropathy, cranial neuropathy (other		
than peripheral n. VII), GB syndrome and myasthenia gravis should be off study.		
Recommended management: See Neurologic Adverse Event Management Algorithm		

Endocrine Hypophysitis Adrenal Insufficiency	Management/Next Dose			
≤ Grade 1	Asymptomatic TSH elevation * Hold pending evaluation, endocrine			
	consult			
	Hold until patients are on a stable replacement hormone regimen. If			
Grade 2	treated with steroids patients must be stable off steroids for two weeks.			
	Resume at same dose level.			
Grade 3	Off study treatment.			
Grade 4	Off protocol therapy			
Note all patients with syn	Note all patients with symptomatic pituitary enlargement, exclusive of hormone deficiency, but			
including severe headach	including severe headache or enlarged pituitary on MRI should be considered grade 3 events. Isolated			
thyroid or testosterone deficiency may be treated as grade 2 if there are no other associated deficiencies				
and adrenal function is monitored.				
Please evaluate pituitary function before beginning steroid therapy or replacement therapy of any kind.				
*Note patients with thyroiditis may be retreated on replacement therapy. Patients must be evaluated to				
rule out pituitary disease prior to initiating thyroid replacement.				
Recommended manage	Recommended management: See Endocrine Management Algorithm			

Creatinine Increased	Management/Next Dose	
≤Grade 1	No change in dose. Monitor toxicity weekly until returned to baseline.	
Grade 2	Hold until \leq Grade 1. Resume at same dose level.	
Grade 3	Hold until \leq Grade 1. Resume at same dose level.	
Grade 4	Off treatment	
Recommended management: See Renal Management Algorithm		

Infusion Reaction	Management/Next Dose		
< Grade 1	Infusion may be slowed or interrupted until symptoms resolve. See		
	Section 5.7 for details on management and subsequent dosing.		
Grade 2	Interrupt until symptoms resolve. See Section 5.7 for details on		

Management/Next Dose		
management and subsequent dosing.		
Immediately discontinue infusion. See Section 5.7 for details on management and subsequent dosing.		

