- Drug will be held for grade 2 cardiac dysfunction pending evaluation
- Drug will be permanently discontinued for grade 3 or 4 cardiac dysfunction and grade 2 events that do not recover to baseline or that reoccur
- Treatment with steroids as clinically indicated

If treatment is delayed > 6 weeks for an adverse event, the patient must be permanently discontinued from study therapy.

Patients requiring high dose steroid treatment for autoimmune or inflammatory events should go off study treatment except for a short course of tapering steroids for infusion reaction, skin rash or endocrine events.

Patients with grade 3 thyroiditis and skin rash may continue therapy with resolution and stable replacement treatment.

Patients with thyroiditis or hypopituitarism who are stable as above may be restarted with replacement hormones including thyroid hormone and physiologic doses of corticosteroids. Please note that grading and for hypophysitis with symptoms of headache, visual or neurologic changes or radiologic evidence of pituitary enlargement and other CNS events such as aseptic meningitis or encephalitis should be considered grade 3 events.

Any patients who require additional immune suppressive treatment beyond steroids should go off study treatment

Patients requiring > two dose delays for the same event should go off protocol therapy.

Prior to starting corticosteroids or hormone replacement for any reason, appropriate endocrine testing including cortisol, ACTH, TSH and T4 must be obtained to document baseline.

Please note that in some cases the treatment algorithms recommend steroids if symptoms do not resolve in 7 days. However, this recommendation is not meant to delay steroid treatment at any time it is clinically indicated.

Patients may be dose-delayed for evaluation and restarted depending on results. Any patient started on corticosteroids initially who is determined to not require steroid treatment for an autoimmune adverse event may resume therapy after a 2 week observation period without further symptoms at the discretion of the PI or investigator.

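### Section 6.1 gives two instructions for grade 3 thyroiditis, and leaves hypophysitis with hormone-deficiency symptoms only unclear

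*Combined protocol and SAP*

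**What the plan says.** **Endocrine table (Section 6.1).** At grade 2 the instruction is "Hold until patients are on a stable replacement hormone regimen", after which treatment resumes at the same dose level. At grade 3 it is "Off study treatment". Three notes follow:

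- Symptomatic pituitary enlargement is counted as grade 3, with hormone deficiency set apart.
- An isolated "thyroid or testosterone deficiency may be treated as grade 2 if there are no other associated deficiencies", provided adrenal function is monitored.
- A footnote says "Note patients with thyroiditis may be retreated on replacement therapy". Its asterisk sits on the lowest-grade row, at asymptomatic TSH elevation, and its text gives no grade limit.

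**Neurologic table note (Section 6.1).** The note begins "Patients with any CNS events including aseptic meningitis, encephalitis, symptomatic" and continues with hypophysitis and several neuropathies. It ends "than peripheral n. VII), GB syndrome and myasthenia gravis should be off study". No grade is given for the hypophysitis.

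**Closing paragraphs (Section 6.1).** "Patients with grade 3 thyroiditis and skin rash may continue therapy with resolution and stable replacement treatment". The next paragraph lets patients with stable thyroiditis or hypopituitarism restart on hormone replacement. It then assigns hypophysitis with headache, visual or neurologic changes, or radiologic pituitary enlargement, to grade 3.

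**Section 5.6.** Patients with drug-related adverse events may resume only if they meet the dose modification criteria in the Section 6 tables.

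**The concern.** A site grading a thyroiditis as grade 3 finds a stop instruction in the table and permission to continue a few paragraphs later. Section 5.6 directs it to the tables, and the permission lies outside them. For hypophysitis with hormone-deficiency symptoms alone, the neurologic and endocrine tables can point in different directions.

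These events are foreseeable. The nivolumab adverse event list in Section 7.1 includes hyperthyroidism, hypothyroidism and hypophysitis, and the varlilumab list includes both thyroid disorders. The reading chosen also matters more in Group 2: Section 6.1 requires both drugs to be held or discontinued together and bars single-agent treatment after an adverse event, so it decides whether all study treatment ends. The error could go either way, with a patient stopped or retreated contrary to the sponsor's intention. At stake is a consistent safety instruction across sites.

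**Working it through.** No arithmetic applies. The check sets the instructions side by side.

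| Event | Stops treatment | Allows continuation or resumption |
|---|---|---|
| Grade 3 thyroiditis | Endocrine grade 3 row; Section 5.6 by its reference to the tables | Closing paragraphs; in part, the table's thyroiditis footnote and isolated-deficiency note |
| Hypophysitis with headache, visual or neurologic changes, or pituitary enlargement | Endocrine grade 3 row, through both grading notes; neurologic note | None |
| Hypophysitis with hormone-deficiency symptoms only | Neurologic note, if its wording is taken without qualification | Endocrine grade 2 row; restart sentence in the closing paragraphs |

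**Grade 3 thyroiditis: does anything in the text settle it?**

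1. *Exception flag.* The All Other Events table marks its grade 3 row as having exceptions listed below it. The endocrine grade 3 row has no such mark.
2. *Thyroiditis footnote.* It is attached to the lowest-grade row. Its wording could reach grade 3 but does not say so.
3. *Isolated-deficiency note.* It moves thyroid deficiency without other deficiencies to the grade 2 row. It does not address thyroiditis that is grade 3 because of hormone excess, or that comes with other deficiencies. The closing sentence has no such limits.
4. *Conflict rules.* One rule in Section 6.1 applies when a patient has several adverse events with conflicting advice. The other ranks Section 6.1 above Appendix D. Neither covers two instructions for one event within Section 6.1.
5. *Section 5.6.* Read literally, it favours the table over the closing text.

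The conflict is therefore softened but not resolved. The skin rash half of the closing sentence is not in dispute: the skin table also holds grade 3 rash and allows resumption at the investigator's discretion.

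**Hypophysitis.** In the second row of the table every instruction agrees, because both grading notes move those cases to grade 3. Only the third row stays open: the endocrine grading note sets hormone deficiency apart, while the neurologic note does not.

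**The case against.** The strongest reply is that Section 6.1 states a general row followed by a specific exception. Thyroid events are treated separately four times: in the footnote, the isolated-deficiency note, the closing sentence and the restart sentence. A patient on stable replacement has by definition a deficiency, which is the case the grade 2 note addresses. Section 6.1 also tells sites to contact the drug monitor about proposed changes, allows clinically justified alternatives and recommends consulting the study PI or drug monitor.

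Much of this stands. A thyroid exception is the more natural reading of Section 6.1 alone, and for isolated deficiency the table and the closing text can agree. It does not remove the problem. The stop instruction applies when the event is graded, which may be before any replacement, and Section 5.6 still limits resumption to the tables. Consultation gives a site a route to an answer without making the written instructions agree.

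A reader might also infer that grade 2 symptomatic hypophysitis in general is both resumed and stopped. The documents do not support that, because hypophysitis with headache, visual or neurologic changes or pituitary enlargement is consistently grade 3 and off treatment. The restart sentence answers much of the deficiency-only case too. What remains turns on whether the neurologic note, which is framed around CNS events, also takes in purely hormonal symptoms.

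**Conclusion.** The text is inconsistent as written on grade 3 thyroiditis, and ambiguous in the narrower case of hypophysitis with hormone-deficiency symptoms only. The inconsistency rests on reading the grade 3 row and Section 5.6 literally; the ambiguity rests on reading the neurologic note without qualification.

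No size can be put on it. The adverse event lists give only broad frequency bands, such as up to 20% for nivolumab's thyroid events and hypophysitis, without grade. A reader might infer a count of affected patients or a shift in an arm's response rate, but the documents support neither. Response is an objective status (Sections 13.1.2 and 13.1.5), and nothing there removes one already recorded when treatment stops. PFS runs from randomization to progression or death (Section 13.4.3), with no censoring at treatment stop stated. Sample size, power and error rates are unaffected. The case for acting is that sites should have one stop-or-continue instruction for a foreseeable immune event.

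**What to change.** Reconcile the passages so that each event has one instruction:

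- In the endocrine grade 3 row, state whether thyroiditis is an exception. If it is, flag it in the row, as the All Other Events table does.
- Give the thyroiditis footnote an explicit grade range, and make the isolated-deficiency note and the closing paragraphs agree with the row.
- State in one place which table governs hypophysitis with hormone-deficiency symptoms only, and cross-refer from the neurologic note.
- In Section 5.6, say whether resumption is governed by the tables alone or by Section 6.1 as a whole, including its notes and closing text.

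Which clinical rule applies is for the sponsor to decide. The cost is a protocol clarification, with no new data and no change to the sample size or analysis.

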7. ADVERSE EVENTS: LIST AND REPORTING REQUIREMENTS

Adverse event (AE) monitoring and reporting is a routine part of every clinical trial. The following list of AEs (Section 7.1) and the characteristics of an observed AE (Sections 7.2 and 7.3) will determine whether the event requires expedited reporting via the CTEP Adverse Event Reporting System (CTEP-AERS) in addition to routine reporting.

7.1 Comprehensive Adverse Events and Potential Risks List(s) (CAEPRs)

7.1.1 CAEPRs for CTEP IND Agent(s)

7.1.1.1 CAEPR for CDX-1127 (Varlilumab)

Comprehensive Adverse Events and Potential Risks list (CAEPR) for CDX-1127 (Varlilumab, NSC 778372)

The Comprehensive Adverse Events and Potential Risks list (CAEPR) provides a single list of reported and/or potential adverse events (AE) associated with an agent using a uniform presentation of events by body system. In addition to the comprehensive list, a subset, the Specific Protocol Exceptions to Expedited Reporting (SPEER), appears in a separate column and is identified with bold and italicized text. This subset of AEs (SPEER) is a list of events that are protocol specific exceptions to expedited reporting to NCI (except as noted below). Refer to the 'CTEP, NCI Guidelines: Adverse Event Reporting Requirements' http://ctep.cancer.gov/protocolDevelopment/electronic_applications/docs/aeguidelines.pdf for further clarification. *Frequency is provided based on 343 patients*. Below is the CAEPR for CDX-1127 (varillumab).

NOTE: Report AEs on the SPEER **ONLY IF** they exceed the grade noted in parentheses next to the AE in the SPEER. If this CAEPR is part of a combination protocol using multiple investigational agents and has an AE listed on different SPEERs, use the lower of the grades to determine if expedited reporting is required.

Version 2.1, September 14, 2019¹

	Adverse Events with Possibl tionship to CDX-1127 (varlilu (CTCAE 5.0 Term) [n= 343]		Specific Protocol Exceptions to Expedited Reporting (SPEER)
Likely (>20%)	Less Likely (<=20%)	Rare but Serious (<3%)	
BLOOD AND LYMPHATIC S	YSTEM DISORDERS		
	Anemia		
CARDIAC DISORDERS			
		Pericardial effusion	
ENDOCRINE DISORDERS	ENDOCRINE DISORDERS		
		Hyperthyroidism	
	Hypothyroidism		
EYE DISORDERS			
		Dry eye	
		Eye disorders - Other (transient central vision loss)	

Adverse Events with Possible Relationship to CDX-1127 (varlilumab) (CTCAE 5.0 Term) [n= 343]			Specific Protocol Exceptions to Expedited Reporting (SPEER)
Likely (>20%)	Less Likely (<=20%)	Rare but Serious (<3%)	
		Eye disorders - Other (visual	
		acuity reduced transiently)	
		Floaters	
		Watering eyes	
GASTROINTESTINAL D	ISORDERS		
		Colitis	
	Diarrhea		Diarrhea (Gr 2)
	Nausea	-	Nausea (Gr 2)
		Proctitis	
	Vomiting		
GENERAL DISORDERS	AND ADMINISTRATION SITE CON	IDITIONS	
F atimus	Chills		
Fatigue			Fatigue (Gr 2)
	Fever		
	Flu like symptoms Malaise		
HEPATOBILIARY DISOF	KDER5	Llenstebilien, die endere	
		Hepatobiliary disorders - Other (hepatitis)	
IMMUNE SYSTEM DISO			
		Allergic reaction	
		Cytokine release syndrome ²	
	ND PROCEDURAL COMPLICATION		
	Infusion related reaction		
INVESTIGATIONS			
	Alanine aminotransferase		
	increased ³		
	Alkaline phosphatase increased ³		
	Aspartate aminotransferase		
	increased		
	Blood bilirubin increased ³		
	GGT increased ³		
	Lipase increased		
	Lymphocyte count decreased		Lymphocyte count decreased (Gr 2)
	Neutrophil count decreased		
	Serum amylase increased		
	Thyroid stimulating hormone		
	increased		
METABOLISM AND NUT		 T	
	Anorexia	Tumor lysis syndrome ⁴	
	ND CONNECTIVE TISSUE DISORE	DERS	
MUSCULUSKELETAL A			
MUSCULUSKELETAL A	Arthralgia		
NERVOUS SYSTEM DIS	· · · · · · · · · · · · · · · · · · ·		

	Adverse Events with Possib tionship to CDX-1127 (varlilu (CTCAE 5.0 Term) [n= 343]		Specific Protocol Exceptions to Expedited Reporting (SPEER)
Likely (>20%)	Less Likely (<=20%)	Rare but Serious (<3%)	
		Nervous system disorders - Other (peripheral sensorimotor neuropathy)	
		Paresthesia	
		Peripheral sensory neuropathy	
RESPIRATORY, THORACIC	AND MEDIASTINAL DISORD	ERS	
		Pneumonitis	
SKIN AND SUBCUTANEOUS	TISSUE DISORDERS		
Pruritus			Pruritus (Gr 2)
Rash maculo-papular			Rash maculo-papular (Gr 2)
		Skin hyperpigmentation	
		Skin hypopigmentation	

¹This table will be updated as the toxicity profile of the agent is revised. Updates will be distributed to all Principal Investigators at the time of revision. The current version can be obtained by contacting [contact]. Your name, the name of the investigator, the protocol and the agent should be included in the e-mail.

²Symptoms of cytokine release syndrome (CRS) and/or allergic reaction may include chills, fever, fatigue, flushing, bronchospasm, and hypotension. In some cases, disseminated intravascular coagulation (DIC), capillary leak syndrome (CLS), and hemophagocytic lymphohistiocytosis/macrophage activation syndrome (HLH/MAS) have been reported in the setting of CRS.

³Symptoms of hepatic dysfunction may include Alanine aminotransferase increased, Alkaline phosphatase increased, Aspartate aminotransferase increased, Blood bilirubin increased, and GGT increased under the INVESTGATIONS SOC.

⁴Tumor lysis syndrome is defined as a massive overload of potassium, phosphate, uric acid, plus hypocalcemia, potentially causing lethal cardiac arrhythmias and/or renal failure.

NOTE: Adverse reactions generally low grade that may represent immune-mediated toxicity, such as rash, diarrhea, fever, and increased liver function tests, have been observed in patients receiving CDX-1127 monotherapy and may be manifestations of immune-mediated adverse events. In clinical trials, most immune-mediated adverse reactions were reversible and managed with interruptions of CDX-1127, administration of corticosteroids and supportive care. Immune-related adverse events which are expected with checkpoint inhibition, have been observed among the patients who have received CDX-1127 (varlilumab) in combination with checkpoint inhibitors.

Adverse events reported on CDX-1127 (varlilumab) trials, but for which there is insufficient evidence to suggest that there was a reasonable possibility that CDX-1127 (varlilumab) caused the adverse event:

BLOOD AND LYMPHATIC SYSTEM DISORDERS - Leukocytosis; Lymph node pain **CARDIAC DISORDERS** - Sinus tachycardia

GASTROINTESTINAL DISORDERS - Abdominal distension; Abdominal pain; Constipation; Dry mouth; Dyspepsia; Dysphagia; Flatulence; Gastroesophageal reflux disease; Gastrointestinal disorders - Other

(tongue discoloration); Gastrointestinal disorders - Other (tongue ulceration); Gastrointestinal pain; Lower gastrointestinal hemorrhage; Mucositis oral; Oral dysesthesia; Oral pain; Periodontal disease; Small intestinal obstruction

GENERAL DISORDERS AND ADMINISTRATION SITE CONDITIONS - Edema limbs; Gait disturbance; General disorders and administration site conditions - Other (temperature intolerance); Localized edema; Non-cardiac chest pain; Pain

INFECTIONS AND INFESTATIONS - Appendicitis; Infections and infestations - Other (candida infection); Infections and infestations - Other (epididymitis); Infections and infestations - Other (Herpes zoster); Mucosal infection; Sepsis; Sinusitis; Thrush

INJURY, POISONING AND PROCEDURAL COMPLICATIONS - Fall; Injury, poisoning and procedural complications - Other (procedural pain)

INVESTIGATIONS - Creatinine increased; Investigations - Other (haptoglobin increased); Investigations - Other (urobilinogen urine increased); Platelet count decreased; Weight loss; White blood cell decreased

METABOLISM AND NUTRITION DISORDERS - Dehydration; Hyperglycemia; Hyperuricemia; Hypocalcemia; Hypoglycemia; Hypokalemia; Hypomagnesemia; Hyponatremia; Hypophosphatemia; Metabolism and nutrition disorders - Other (cachexia); Metabolism and nutrition disorders - Other (hyperalbuminemia); Metabolism and nutrition disorders - Other (malnutrition)

MUSCULOSKELETAL AND CONNECTIVE TISSUE DISORDERS - Back pain; Flank pain; Generalized muscle weakness; Muscle cramp; Musculoskeletal and connective tissue disorder - Other (axillary pain); Musculoskeletal and connective tissue disorder - Other (groin pain); Musculoskeletal and connective tissue disorder - Other (osteolysis); Musculoskeletal and connective tissue disorder - Other (pain in jaw); Myalgia; Neck pain; Pain in extremity

NEOPLASMS BENIGN, MALIGNANT AND UNSPECIFIED (INCL CYSTS AND POLYPS) - Tumor pain NERVOUS SYSTEM DISORDERS - Dizziness; Dysgeusia; Lethargy

PSYCHIATRIC DISORDERS - Insomnia; Irritability; Personality change

RENAL AND URINARY DISORDERS - Acute kidney injury; Chronic kidney disease; Hematuria; Renal and urinary disorders - Other (urine odor abnormal); Urinary frequency

RESPIRATORY, THORACIC AND MEDIASTINAL DISORDERS - Allergic rhinitis; Bronchopulmonary hemorrhage; Bronchospasm; Cough; Dyspnea; Nasal congestion; Oropharyngeal pain; Respiratory failure; Sinus pain; Sneezing; Voice alteration; Wheezing

SKIN AND SUBCUTANEOUS TISSUE DISORDERS - Alopecia; Bullous dermatitis; Dry skin; Erythroderma; Hyperhidrosis; Pain of skin; Palmar-plantar erythrodysesthesia syndrome; Rash acneiform; Skin and subcutaneous tissue disorders - Other (pemphigoid); Skin and subcutaneous tissue disorders -Other (skin hemorrhage)

VASCULAR DISORDERS - Flushing; Hot flashes; Hypertension; Hypotension

Note: CDX-1127 (varlilumab) in combination with other agents could cause an exacerbation of any adverse event currently known to be caused by the other agent, or the combination may result in events never previously associated with either agent.

7.1.1.2 CAEPR for Nivolumab

Comprehensive Adverse Events and Potential Risks list (CAEPR) for Nivolumab (NSC 748726)

The Comprehensive Adverse Events and Potential Risks list (CAEPR) provides a single list of reported and/or potential adverse events (AE) associated with an agent using a uniform presentation of events by body system. In addition to the comprehensive list, a subset, the Specific Protocol Exceptions to Expedited Reporting (SPEER), appears in a separate column and is identified with bold and italicized text. This subset of AEs (SPEER) is a list of events that are protocol specific exceptions to expedited reporting to NCI (except as noted below). Refer to the 'CTEP, NCI Guidelines: Adverse Event Reporting Requirements' http://ctep.cancer.gov/protocolDevelopment/electronic_applications/docs/aeguidelines.pdf

for further clarification. *Frequency is provided based on 2069 patients*. Below is the CAEPR for Nivolumab.

NOTE: Report AEs on the SPEER **ONLY IF** they exceed the grade noted in parentheses next to the AE in the SPEER. If this CAEPR is part of a combination protocol using multiple investigational agents and has an AE listed on different SPEERs, use the lower of the grades to determine if expedited reporting is required.

		Version 2	2.4, December 2, 2020 ¹
Adverse Events with Possible Relationship to Nivolumab (CTCAE 5.0 Term) [n= 2069]			Specific Protocol Exceptions to Expedited Reporting (SPEER)
Likely (>20%)	Less Likely (<=20%)	Rare but Serious (<3%)	
BLOOD AND LYMPHAT	IC SYSTEM DISORDERS		
	Anemia		Anemia (Gr 3)
CARDIAC DISORDERS			
		Cardiac disorders - Other (cardiomyopathy)	
		Myocarditis	
		Pericardial tamponade ²	
		Pericarditis	
ENDOCRINE DISORDE			
	Adrenal insufficiency ³		
	Hyperthyroidism ³		
	Hypophysitis ³		
	Hypothyroidism ³		
EYE DISORDERS			
		Blurred vision	
		Dry eye	
		Eye disorders - Other (diplopia) ³	
		Eye disorders - Other (Graves ophthalmopathy) ³	
		Eye disorders - Other (optic neuritis retrobulbar) ³	
		Eye disorders - Other (Vogt- Koyanagi-Harada)	
	Uveitis		
GASTROINTESTINAL D	ISORDERS		
	Abdominal pain		Abdominal pain (Gr 2)
	Colitis ³		
		Colonic perforation ³	
	Diarrhea		Diarrhea (Gr 3)
	Dry mouth		Dry mouth (Gr 2)
		Enterocolitis	
		Gastritis	
		Mucositis oral	
	Nausea		Nausea (Gr 2)
	Pancreatitis ⁴		
	AND ADMINISTRATION SITE	CONDITIONS	
Fatigue			Fatigue (Gr 3)
	Fever		Fever (Gr 2)
	Injection site reaction		Injection site reaction (Gr 2)

Adverse Events with Possible Relationship to Nivolumab (CTCAE 5.0 Term) [n= 2069]			Specific Protocol Exceptions to Expedited Reporting (SPEER)
Likely (>20%)	Less Likely (<=20%)	Rare but Serious (<3%)	
HEPATOBILIARY DISOR	DERS		
		Hepatobiliary disorders - Other (immune-mediated hepatitis)	
IMMUNE SYSTEM DISOF	RDERS		
		Allergic reaction ³	
		Autoimmune disorder ³	
		Cytokine release syndrome ⁵	
		Immune system disorders - Other (GVHD in the setting of allotransplant) ^{3,6}	
		Immune system disorders - Other (sarcoidosis) ³	
INJURY, POISONING AN	D PROCEDURAL COMPLICA	TIONS	
	Infusion related reaction ⁷		
INVESTIGATIONS			
	Alanine aminotransferase increased ³		Alanine aminotransferase increased ³ (Gr 3)
	Aspartate aminotransferase increased ³		Aspartate aminotransferase increased ³ (Gr 3)
	Blood bilirubin increased ³		Blood bilirubin increased ³ (Gr 2)
	CD4 lymphocytes decreased		CD4 lymphocyte decreased (Gr 4)
	Creatinine increased		
	Lipase increased		
	Lymphocyte count decreased		Lymphocyte count decreased (Gr 4)
	Neutrophil count decreased		
	Platelet count decreased		
	Serum amylase increased		
METABOLISM AND NUTI	RITION DISORDERS		
	Anorexia		
		HyperglycemiaMetabolism and nutritiondisorders - Other (diabetesmellitus with ketoacidosis)3	Hyperglycemia (Gr 2)
MUSCULOSKELETAL AN	ID CONNECTIVE TISSUE DIS	ÓRDERS	
	Arthralgia		
		Musculoskeletal and connective tissue disorder - Other (polymyositis)	
		Myositis	
		Rhabdomyolysis	
NERVOUS SYSTEM DISC	JRDERS	Encombolog -41-3	
		Encephalopathy ³	
		Facial nerve disorder ³ Guillain-Barre syndrome ³	
		·	
		Myasthenia gravis ³	

Adverse Events with Possible Relationship to Nivolumab (CTCAE 5.0 Term) [n= 2069]			Specific Protocol Exceptions to Expedited Reporting (SPEER)
Likely (>20%)	Less Likely (<=20%)	Rare but Serious (<3%)	
		Nervous system disorders - Other (demyelination myasthenic syndrome)	
		Nervous system disorders - Other (encephalitis) ³	
		Nervous system disorders - Other (meningoencephalitis)	
		Nervous system disorders - Other (meningoradiculitis) ³	
		Nervous system disorders - Other (myasthenic syndrome)	
		Peripheral motor neuropathy	
		Peripheral sensory neuropathy	
		Reversible posterior leukoencephalopathy syndrome ³	
RENAL AND URINARY DI	SORDERS		
		Acute kidney injury ³	
		Renal and urinary disorders - Other (immune-mediated nephritis)	
RESPIRATORY, THORAC	IC AND MEDIASTINAL DISOF		
,	Pleural effusion ³		
	Pneumonitis ³		
		Respiratory, thoracic and mediastinal disorders - Other (bronchiolitis obliterans with organizing pneumonia) ³	
SKIN AND SUBCUTANEO	US TISSUE DISORDERS		
		Erythema multiforme ³	
	Pruritus ³		Pruritus ³ (Gr 2)
	Rash maculo-papular ³		Rash maculo-papular ³ (Gr 2)
		Skin and subcutaneous tissue disorders - Other (bullous pemphigoid)	
	Skin and subcutaneous tissue disorders - Other (Sweet's Syndrome) ³		
	Skin hypopigmentation ³		
		Stevens-Johnson syndrome	
		Toxic epidermal necrolysis	

¹This table will be updated as the toxicity profile of the agent is revised. Updates will be distributed to all Principal Investigators at the time of revision. The current version can be obtained by contacting [contact]. Your name, the name of the investigator, the protocol and the agent should be included in the e-mail.

²Pericardial tamponade may be related to possible inflammatory reaction at tumor site.

³Nivolumab being a member of class of agents involved in the inhibition of "immune checkpoints", may result in severe and possibly fatal immune-mediated adverse events probably due to T-cell activation and proliferation. This may result in autoimmune disorders that can include (but are not limited to) autoimmune hemolytic anemia, acquired anti-factor VIII immune response, autoimmune aseptic meningitis, autoimmune hepatitis, autoimmune nephritis, autoimmune neuropathy, autoimmune thyroiditis, bullous pemphigoid, exacerbation of Churg-Strauss Syndrome, drug rash with eosinophilia systemic symptoms [DRESS] syndrome, facial nerve disorder (facial nerve paralysis), limbic encephalitis, hepatic failure, pure red cell aplasia, pancreatitis, ulcerative and hemorrhagic colitis, endocrine disorders (e.g., autoimmune thyroiditis, hyperthyroidism, hypothyroidism, autoimmune hypophysitis/hypopituitarism, thyrotoxicosis, and adrenal insufficiency), sarcoid granuloma, myasthenia gravis, polymyositis, and Guillain-Barre syndrome.

⁴Pancreatitis may result in increased serum amylase and/or more frequently lipase.

⁵Cytokine release syndrome may manifest as hemophagocytic lymphohistiocytosis with accompanying fever and pancytopenia.

⁶Complications including hyperacute graft-versus-host disease (GVHD), some fatal, have occurred in patients receiving allo stem cell transplant (SCT) after receiving Nivolumab. These complications may occur despite intervening therapy between receiving Nivolumab and allo-SCT.

⁷Infusion reactions, including high-grade hypersensitivity reactions which have been observed following administration of nivolumab, may manifest as fever, chills, shakes, itching, rash, hypertension or hypotension, or difficulty breathing during and immediately after administration of nivolumab.

Adverse events reported on Nivolumab trials, but for which there is insufficient evidence to suggest that there was a reasonable possibility that Nivolumab caused the adverse event:

BLOOD AND LYMPHATIC SYSTEM DISORDERS - Leukocytosis

CARDIAC DISORDERS - Atrial fibrillation; Atrioventricular block complete; Heart failure; Ventricular arrhythmia

EAR AND LABYRINTH DISORDERS - Vestibular disorder

EYE DISORDERS - Eye disorders - Other (iridocyclitis); Optic nerve disorder; Periorbital edema **GASTROINTESTINAL DISORDERS** - Constipation; Duodenal ulcer; Flatulence; Gastrointestinal disorders - Other (mouth sores); Vomiting

GENERAL DISORDERS AND ADMINISTRATION SITE CONDITIONS - Chills; Edema limbs; Malaise; Pain

HEPATOBILIARY DISORDERS - Bile duct stenosis

IMMUNE SYSTEM DISORDERS - Anaphylaxis; Immune system disorders - Other (autoimmune thrombotic microangiopathy); Immune system disorders - Other (limbic encephalitis)

INFECTIONS AND INFESTATIONS - Bronchial infection; Lung infection; Sepsis; Upper respiratory infection

INVESTIGATIONS - Blood lactate dehydrogenase increased; GGT increased; Investigations - Other (protein total decreased); Lymphocyte count increased; Weight loss

METABOLISM AND NUTRITION DISORDERS - Dehydration; Hyperuricemia; Hypoalbuminemia; Hypocalcemia; Hyponatremia; Hypophosphatemia

MUSCULOSKELETAL AND CONNECTIVE TISSUE DISORDERS - Back pain; Musculoskeletal and connective tissue disorder - Other (musculoskeletal pain); Musculoskeletal and connective tissue disorder - Other (polymyalgia rheumatica); Myalgia; Pain in extremity

NEOPLASMS BENIGN, MALIGNANT AND UNSPECIFIED (INCL CYSTS AND POLYPS) - Neoplasms benign, malignant and unspecified (incl cysts and polyps) - Other (Histiocytic necrotizing lymphadenitis) NERVOUS SYSTEM DISORDERS - Dizziness; Headache; Intracranial hemorrhage PSYCHIATRIC DISORDERS - Insomnia

RENAL AND URINARY DISORDERS - Hematuria; Renal and urinary disorders - Other (tubulointerstitial

nephritis)

RESPIRATORY, THORACIC AND MEDIASTINAL DISORDERS - Bronchospasm; Cough; Dyspnea; Hypoxia

SKIN AND SUBCUTANEOUS TISSUE DISORDERS - Alopecia; Dry skin; Hyperhidrosis; Pain of skin; Photosensitivity; Rash acneiform; Skin and subcutaneous tissue disorders - Other (rosacea) VASCULAR DISORDERS - Flushing; Hypertension; Hypotension; Vasculitis

Note: Nivolumab in combination with other agents could cause an exacerbation of any adverse event currently known to be caused by the other agent, or the combination may result in events never previously associated with either agent.

